5.3 Point of Enrollment

The point of enrollment occurs when a participant has provided written informed consent and an energy delivery has been attempted during the index procedure.

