41. Uncontrolled hyperglycemia with a glucose level >270 mg/dl (>15 mmol/L) after an overnight fast or >360 mg/dl (>20 mmol/l) in a randomly performed measurement that is confirmed by a second measurement (not on the same day) since screening visit
42. Mean of 3 separate blood pressure measurements >180 mmHg (systolic) or >100 mmHg (diastolic)
43. Women of child-bearing potential with a positive urine pregnancy test at baseline visit
44. Grade III or greater esophagitis on endoscopy
45. Abnormalities of the GI tract preventing endoscopic access to the duodenum
46. Anatomic abnormalities in the duodenum that would preclude the completion of the treatment procedure, including tortuous anatomy
47. Endoscopic observation of upper gastrointestinal abnormality such as ulcers, duodenal polyps in the area to be treated, varices, strictures, congenital or intestinal telangiectasia
48. Any other anatomical or endoscopic abnormalities/characteristics that, in the opinion of the investigator, would preclude safe use of the investigational device or procedure.

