5.4 Screen Failures

Screen failures are defined as participants who consented to participate in the clinical study and started the screening tests specified by the protocol but are not subsequently enrolled in the study. Screen failure information including demography, screen failure details, eligibility criteria, and any serious adverse event (SAE) will be documented on eCRFs.

Individuals who do not meet the criteria for participation in this study (screen failure) may be rescreened. Data from all screen and re-screen visits will be captured on eCRFs.

Individuals who failed at endoscopic screening will be followed for 30 days for safety.

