6 STUDY INTERVENTION AND CONCOMITANT THERAPY

6.1 Study Intervention (Index Procedure)

The study intervention is the duodenal mucosal regeneration (DMR) procedure using the Endogenex device.

The DMR procedure is performed under general anesthesia or deep sedation. Participants will be prepared for anesthesia and upper endoscopy according to institution's standard practice.

At the beginning of the procedure, participants will undergo endoscopic assessment to confirm endoscopic eligibility. Participants who meet the endoscopic eligibility will undergo the DMR procedure following the procedure steps described in the Instruction for Use (IFU). In brief, the catheter is inserted trans-orally into the participant's duodenum under endoscopic visualization. Fluoroscopy maybe used to guide the catheter insertion when needed. The catheter's flex circuit section is positioned approximately 2cm distal to the Papilla of Vater. The flex circuit board is deployed to achieve contact between the duodenal wall and the electrodes on the circuit board. Energy delivery is initiated by pressing the "Start" button on the generator. Upon completion of energy delivery, the circuit board is retracted into the housing in a compressed configuration and moved distally (or proximally) to the next treatment zone. The procedure is repeated until the desired treatment length is achieved. The thermal markers on the circuit board will create tissue markers that identify the proximal and distal end of each treatment zone, which facilitates index of the treatment zone. Upon completion of the treatment, the catheter is removed, and a final endoscopic inspection is performed.

Participant will be recovered from anesthesia, monitored in the recovery room per local standard protocol, and discharged according to local institution's discharge criteria and procedures. An overnight stay is not required but permitted per investigator's clinical judgement.

Before the participant is discharged, s/he is to be provided with a study information card. This card provides the phone number and name of the person to contact in case s/he needs medical attention related to the therapy. Additionally, the participant can provide this card to an emergency room doctor, allowing them to contact the Primary Investigator and obtain information about the study. A sample of the card is provided in **Appendix 3**.

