11.3 Analysis Populations

The following analysis populations are defined for the study: Intent-to-Treat (ITT), modified Intent-to-Treat (mITT), Per-Protocol (PP) and Completed Cases (CC). The primary safety analysis will be performed on the ITT population. The primary effectiveness analysis will be performed on mITT population.

- Intent-to-Treat: The Intent-to-Treat population includes all enrolled participants as defined in Section 5.3 regardless of whether or not the participant received the full treatment.
- Modified Intent-to-Treat: The mITT population consists of the ITT population participants who received the target treatment (at least 6 cm of duodenum treatment) and that have at least one post-treatment follow-up.
- Per-Protocol: The Per-Protocol population is a subset of the mITT population and includes all participants who received the target treatment, do not have any major eligibility violations, and maintained stable glucose-lowering medications for 24 weeks post procedure.

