5. STUDY OVERVIEW

5.1. Study Design and Description of the Study Device

This is a multicenter, open-label, treatment-only study conducted in the United States. A total of 20 participants is planned for the study. The study will test two treatment parameters. The first 10 participants will be treated at a generator setting of 600 Volts/13 bursts/350 KHz (600V) and the second group of 10 participants at 750 Volts/8 bursts/350KHz (750V). In the 600V group, the first 5 participants will be enrolled/treated with the investigational device sequentially with at least 14 days observation time between each procedure. In the 750V group, the first participants will be enrolled/treated with the investigational device sequentially with at least 6 days observation time between each procedure.

Participants with T2D inadequately controlled on 2-3 non-insulin glucose-lowering medication(s) will be screened for study eligibility. Eligible participants who consent to participate in the study will maintain his/her background glucose-lowering medication(s) stable (no medication or dose change) for at least 12 weeks prior to baseline visit.

The index procedure will be performed under general anesthesia or deep sedation and within 21 days from the baseline visit. Participants will undergo endoscopic screening immediately prior to the DMR procedure, and eligible participants will undergo the DMR procedure. Participants may be discharged per local hospital's guideline; an overnight stay is not required but allowed per local policy and investigator's clinical judgement. A participant is enrolled in the study when the Endogenex catheter insertion is attempted. Participants excluded during endoscopic screening will be considered a screen failure and will be followed for four weeks after the procedure for safety.

Post index procedure, participants will be on a transitional diet consisting of clear liquids for 24 hours followed by a full liquid diet for 3 days, pureed food for 3 days, and soft food for one week, and then return to normal food as tolerated.

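### A patient in whom the catheter is inserted but no energy is attempted is never enrolled, so a related SAE at that stage falls outside the primary safety proportion

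*Protocol*

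**What the plan says.** Protocol 5.3 fixes enrolment late in the procedure: "The point of enrollment occurs when a participant has provided written informed consent and an energy delivery has been attempted during the index procedure". The Protocol Summary and sections 4.1, 4.2 and 6.1 also tie enrolment to attempted energy delivery. In section 6.1 endoscopic eligibility is confirmed first. Then "the catheter is inserted trans-orally into the participant's duodenum under endoscopic visualization", it is positioned beyond the papilla, the circuit is deployed, and only after that is energy started.

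The analysis sets follow from the enrolment point. Protocol 11.3: "The Intent-to-Treat population includes all enrolled participants as defined in Section 5.3". Sections 11.3 and 11.4.2 run the primary safety endpoint on ITT.

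Under Protocol 5.4, screen failures are people who consented and "started the screening tests specified by the protocol but are not subsequently enrolled in the study". For them, "Screen failure information including demography, screen failure details, eligibility criteria, and any serious adverse event (SAE) will be documented on eCRFs". Follow-up is narrower: "Individuals who failed at endoscopic screening will be followed for 30 days for safety". Section 4.1 also says 30 days; the Summary and sections 4.2 and 6.1 say four weeks.

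The SAP's ITT definition (sections 3 and 6) repeats the energy-delivery rule, but other SAP text uses different triggers. Section 5.1 has "A participant is enrolled in the study when the Endogenex catheter insertion is attempted". Section 3 has endoscopic screening passed and the patient proceeding to the index procedure. The opening of section 6 has endoscopic screening passed. Section 10 defines the safety ITT by endoscopic screening having been initiated.

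Procedure success means at least 6 cm of duodenum treated (Protocol 3). Protocol 11.4.3 analyses secondary endpoints primarily in mITT, and SAP 9 assigns procedure success to FAS. Both sets admit only patients with at least 6 cm treated.

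**The concern.** The objectives are device safety and technical feasibility in a first-in-human study. Protocol 2.5.2 lists upper GI trauma, perforation and inability to remove the device among anticipated harms, and each could occur before any energy is delivered. The primary endpoint counts device- or procedure-related SAEs, not only energy-related ones. Protocol 9.1 dates adverse device effects from exposure to the device, and Protocol 3 starts procedure time at catheter insertion. By the protocol's own concepts, then, a patient with the catheter inserted has been exposed and the procedure has begun.

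Conditioning the safety set on the device having been placed and deployed removes the attempts that went worst at the placement stage. Any resulting bias in the SAE proportion favours the device when the omitted patients carry related SAEs. The same patients are relevant to feasibility: Appendix 5 says the second-generation catheter was introduced partly to fit a broader range of duodenal diameters.

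**Working it through.** **Classifying the patient.** Take someone who consents, passes endoscopy and has the catheter inserted, but in whom the attempt is abandoned before energy is started.

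1. Protocol 5.3: no energy attempted, so not enrolled.
2. Protocol 5.4: consented, screened and not enrolled, so a screen failure. Any SAE goes on the eCRF.
3. Protocol 11.3: not enrolled, so not in ITT.
4. Protocol 11.4.2: the primary proportion uses ITT, so the patient is in neither numerator nor denominator.
5. Protocol 5.4 follow-up: it is written for failures at endoscopic screening, and this patient passed. Either stated period (30 days or four weeks = 28 days) is also shorter than the 12-week horizon (84 days).
6. The SAP's ITT definition gives the same answer as step 3. Its section 5.1, the enrolment sentences in sections 3 and 6, and section 10 would count the patient.

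**Procedure success.** Success is at least 6 cm treated, and mITT/FAS membership requires at least 6 cm treated. Successes divided by patients in mITT/FAS is therefore n/n = 100% for any data and any enrolment point. An enrolled patient treated over less than 6 cm is dropped as well. SAP 9 says such patients count as failures, but names a population that cannot contain them.

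**Size.** There is no plan figure to reproduce: Protocol 11.2 justifies 20 participants by the feasibility nature of the study, with no formula, and 11.4.2 tests no hypothesis. The illustration uses that 20, all assumed fully treated with no related SAE, plus an assumed k patients with the catheter inserted and no energy attempted.

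Exact (Clopper-Pearson) 95% limits for x/n are the 0.025 quantile of Beta(x, n-x+1) and the 0.975 quantile of Beta(x+1, n-x). At the extremes, the upper limit for 0/20 is 1 - 0.025^(1/20) = 16.8%, and the lower limit for 20/20 is 0.025^(1/20) = 83.2%.

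| Assumption | Related SAE | Success |
|---|---|---|
| As planned (k not counted) | 0/20 = 0% (0-16.8) | 20/20 = 100% (83.2-100) |
| k = 2, one with SAE | 1/22 = 4.5% (0.1-22.8) | 20/22 = 90.9% (70.8-98.9) |
| k = 1, with SAE | 1/21 = 4.8% (0.1-23.8) | 20/21 = 95.2% (76.2-99.9) |
| k = 2, both with SAE | 2/22 = 9.1% (1.1-29.2) | 20/22 = 90.9% (70.8-98.9) |
| k = 3, all with SAE | 3/23 = 13.0% (2.8-33.6) | 20/23 = 87.0% (66.4-97.2) |

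If k = 2 and neither has an SAE, the safety result is 0/22, with upper limit 1 - 0.025^(1/22) = 15.4%; only success changes materially.

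**Chance that the case arises.** With q the assumed probability of failure before energy, the chance of at least one in 20 attempts is 1 - (1-q)^20: 33% at q = 2%, 64% at 5% and 88% at 10%. The documents give no value for q.

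**The case against.** The strongest reply is that safety oversight is largely intact. SAEs in screen failures are recorded (Protocol 5.4), SAEs go to the sponsor within 36 hours (9.3.2), related AEs are followed until resolution or stabilization (9.1), and an independent monitor adjudicates device-related SAEs (10). That stands: the event leaves the endpoint, not the database. What remains missing is its place in the primary proportion, and scheduled surveillance to Week 12 for events that appear late.

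Four stronger readings are tempting, and the documents do not support them.

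- A reader might infer that any catheter injury is lost. It is not if energy is later attempted: 11.4.2 counts events at or after the index procedure, and 6.1 places insertion within that procedure.
- A reader might blame the enrolment point for the 100% success rate. The mITT/FAS filter produces it anyway.
- A reader might suspect that a failed passage could be reclassified afterwards under exclusion 46 ("Anatomic abnormalities in the duodenum that would preclude the completion of the treatment procedure, including tortuous anatomy"). Section 5.2 says this group of criteria is confirmed during screening, 4.1, 4.2 and 6.1 place endoscopic eligibility before the DMR procedure, and nothing permits reclassification later.
- A reader might take the 100% success and absence of related SAEs in 27 treated patients (Appendix 4, section 1) as a sign of hidden failures. No failure before energy is reported, and those figures are no evidence either way.

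It is also fair that the SAP is written for REGENT-1-US, Doc. No. 346, and not for protocol 196. Its section 5.1 is therefore weak authority for changing this protocol; the case rests on the protocol's own text.

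**Conclusion.** The point holds for one narrow group: catheter inserted, no energy attempted. Under the protocol, and under the SAP's ITT definition, these patients are outside the primary safety proportion and have no clear scheduled follow-up to Week 12. The conflicting SAP triggers do not resolve this. Procedure success omits them too, but its main defect is the mITT/FAS denominator, which moving enrolment alone would not repair.

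The size is unknown. In the two-patient illustration the SAE estimate moves from 0% to 4.5% with heavily overlapping intervals, and success from 100% to 90.9%. If no such patient exists, the safety result is unchanged. Since the study only describes outcomes, no test or decision rule is affected; what is affected is whether the reported proportions cover everyone exposed to the device. This is a worthwhile, low-cost correction, not a threat to the study as a whole.

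**What to change.** 1. In Protocol 4.1, 4.2, 5.3, 6.1 and 11.3 (and the matching Summary text), and in SAP 3, 5.1, 6 and 10, use one trigger for enrolment and ITT: attempted insertion of the Endogenex catheter after endoscopic eligibility has been confirmed.
2. Use that set for the primary safety endpoint. Follow every patient in it for device- or procedure-related SAEs to Week 12, including those who receive no energy, counting from the day of attempted insertion.
3. In Protocol 11.4.3 and SAP 9 and 9.2, analyse procedure success in that set instead of mITT/FAS. Count patients with no energy delivered, or with less than 6 cm treated, as failures. mITT/FAS can stay for the glycemic endpoints.
4. Report how many patients had the catheter inserted without an energy attempt, even if the number is zero.

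The cost is wording in both documents and safety follow-up of a few extra patients. The downside for the sponsor is that the safety and success figures may look slightly less favourable.

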5.4 Screen Failures

Screen failures are defined as participants who consented to participate in the clinical study and started the screening tests specified by the protocol but are not subsequently enrolled in the study. Screen failure information including demography, screen failure details, eligibility criteria, and any serious adverse event (SAE) will be documented on eCRFs.

Individuals who do not meet the criteria for participation in this study (screen failure) may be rescreened. Data from all screen and re-screen visits will be captured on eCRFs.

Individuals who failed at endoscopic screening will be followed for 30 days for safety.

6 STUDY INTERVENTION AND CONCOMITANT THERAPY

6.1 Study Intervention (Index Procedure)

The study intervention is the duodenal mucosal regeneration (DMR) procedure using the Endogenex device.

The DMR procedure is performed under general anesthesia or deep sedation. Participants will be prepared for anesthesia and upper endoscopy according to institution's standard practice.

At the beginning of the procedure, participants will undergo endoscopic assessment to confirm endoscopic eligibility. Participants who meet the endoscopic eligibility will undergo the DMR procedure following the procedure steps described in the Instruction for Use (IFU). In brief, the catheter is inserted trans-orally into the participant's duodenum under endoscopic visualization. Fluoroscopy maybe used to guide the catheter insertion when needed. The catheter's flex circuit section is positioned approximately 2cm distal to the Papilla of Vater. The flex circuit board is deployed to achieve contact between the duodenal wall and the electrodes on the circuit board. Energy delivery is initiated by pressing the "Start" button on the generator. Upon completion of energy delivery, the circuit board is retracted into the housing in a compressed configuration and moved distally (or proximally) to the next treatment zone. The procedure is repeated until the desired treatment length is achieved. The thermal markers on the circuit board will create tissue markers that identify the proximal and distal end of each treatment zone, which facilitates index of the treatment zone. Upon completion of the treatment, the catheter is removed, and a final endoscopic inspection is performed.

Participant will be recovered from anesthesia, monitored in the recovery room per local standard protocol, and discharged according to local institution's discharge criteria and procedures. An overnight stay is not required but permitted per investigator's clinical judgement.

Before the participant is discharged, s/he is to be provided with a study information card. This card provides the phone number and name of the person to contact in case s/he needs medical attention related to the therapy. Additionally, the participant can provide this card to an emergency room doctor, allowing them to contact the Primary Investigator and obtain information about the study. A sample of the card is provided in **Appendix 3**.

The participant will be placed on a clear liquid diet for 24 hours, followed by full liquid diet for 3 days, pureed food for 3 days, soft food for one week, and then return to normal food as tolerated.

Antiemetic (such as Ondansetron) and antispasmodics (such as Butylscopolamine) may be provided on standby following the DMR procedure, and the participants should be educated on their use.

Participants who are excluded during endoscopic screening will be considered a screening failure and be followed for four weeks for safety.

A participant is considered enrolled in the study when the participant has given written informed consent and the energy delivery is attempted.

6.2 Glucose-Lowering Medications

Participants will be seen by the treating physician for diabetes review and medication management starting from screening visits and throughout the study.

6.2.1 Background Glucose-Lowering Medications

Eligible participants must be on one to four non-insulin glucose-lowering medication(s) without a severe hypoglycemic event within the past six months of the screening visit.

Participant's background medication will be kept stable (no change in medication or dose) for at least 12 weeks prior to the Baseline Visit.

Peri-procedurally, the dose of medications with hypoglycemic risks will be adjusted per guidelines provided in **Section 6.2.2**.

During the transitional diet period, participant's medication will be titrated to the background level and maintained stable until the Week 24 Visit has been completed. Medication and/or dose change necessary for managing hypoglycemia, hyperglycemia, or other safety concerns is permitted. Reason for the medication change must be documented on eCRF.

Following the Week 24 Visit, participants will be managed according to the current (2020) guidelines of the American Diabetes Association² and their glucose-lowering medications will be optimized as necessary to reach an HbA1c target of 7%.

Background medications are non-investigational products. They should be used in accordance with standard of care and their approved labeling. They will not be provided by the sponsor except if required by local regulations.

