3 STUDY OBJECTIVES AND ENDPOINTS

The objective of this first-in-human study is to assess the feasibility and preliminary safety of the Endogenex device for endoscopic duodenal mucosal regeneration in individuals with type 2 diabetes inadequately controlled on glucose-lowering medications.

The study will also assess, as exploratory endpoints, treatment efficacy, evaluated by changes in glycemic control and liver enzymes post procedure from baseline.

Objectives	Endpoints
Primary 
 • To assess the safety of the Endogenex device for DMR procedure 	
 • Proportion of participants experiencing one or more device- or procedure-related serious adverse events at 12 weeks post procedure.
Secondary 
 • To assess the technical feasibility of the Endogenex device for DMR procedure • To assess changes in glycemic control • To assess changes in liver enzymes 	
 • Procedure success: defined as successful treatment of at least 6 cm of duodenum segment. • Procedure time: defined as the time between the Endogenex catheter insertion and the catheter removal. • Change from baseline in glycemic parameters post index procedure, by visits 
 ○ HbA1c ○ Fasting plasma glucose (FPG) ○ Insulin-resistance by HOMA-IR ○ Post prandial plasma glucose (PPG), Beta cell function, disposition index by mixed meal tolerance test (MMTT) • Proportion of treated participants with an HbA1c improvement of 0.3% or more at 24 weeks from baseline • Proportion of treated participants with an HbA1c improvement of 0.3% or more at 24 weeks from baseline and maintained at 48 weeks • Change in weight from baseline by visit • Change in glucose-lowering medication usage • Change in liver enzyme from baseline at 24 weeks 
 ○ Alanine Aminotransferase (ALT) ○ Aspartate Aminotransferase (AST) • Change from baseline in blood pressure and lipid profile by visit

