4 STUDY DESIGN

4.1 Study Design

This is a multicenter, single-arm, open-label study conducted in Australia. The study enrolls participants inadequately controlled on non-insulin medications (NIS Cohort) and on basal insulin (IS Cohort). The NIS Cohort is described below. The IS Cohort is described in **Appendix 4**.

Twenty (20) participants will be enrolled initially and up to 60 participants may be enrolled in NIS Cohort. The first 30 participants will be treated with the first-generation catheter (Gen 1) and the next 20-30 participants will be treated with the second-generation device (Gen 2). Patients who sign the informed consent and are deemed eligible following a general and endoscopic screening will be enrolled in the study.

Participants with T2D inadequately controlled on 1-4 non-insulin glucose-lowering medication(s) will be screened for study eligibility. Eligible participants who consent to participate in the study will maintain his/her background glucose-lowering medication(s) stable (no medication or dose change) for at least 12 weeks prior to baseline visit.

The index procedure will be performed under general anesthesia or deep sedation and within 28 days from the baseline visit. Participants will undergo endoscopic screening immediately prior to the DMR procedure, and eligible participants will undergo the DMR procedure. Participants may be discharged per local hospital's guideline; an overnight stay is not required but allowed per local policy and investigator's clinical judgement. A participant is enrolled in the study when an energy delivery is attempted. Participants excluded during endoscopic screening will be considered a screen failure and will be followed for 30 days after the procedure for safety.

Post index procedure, participant will be on a transitional diet consisting of clear liquids for 24 hours followed by full liquid diet for 3 days, pureed food for 3 days, and soft food for one week.

Background medication will be titrated to the pre-procedure dose and maintained for 24 weeks post index procedure and the transitional diet period per Section 6.2. After the 24-week follow-up visit, participants will be managed according to the current (2020) guidelines of the American Diabetes Association² and their glucose-lowering medications will be optimized to achieve individualized A1c goals, which for most individuals is a target of less than 7.0%.

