5.1 Inclusion Criteria

Participants are eligible to be included in the study only if all of the following criteria apply:

1. 18-70 years of age
2. Current diagnosis of T2D
3. History of T2D for less than or equal to 10 years
4. HbA1C of 7.5-11.0% (58 - 97 mmol/mol), inclusive
5. BMI 24-40 kg/m², inclusive
6. On stable non-insulin glucose lowering medications (1-4 medications) for at least 12 weeks prior to baseline visit
7. Weight stability (defined as a < 5% change in body weight) for at least 12 weeks prior to the screening visit
8. Agree not to donate blood during participation in the study.
9. Able to comply with study requirements and understand and sign the Informed Consent Form
10. Women of childbearing potential must be using an acceptable method of contraception throughout the study
11. Willing and able to perform self-monitoring blood glucose and comply with study visits and study tasks as required per protocol.

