6.2.3 Rescue Criteria

Participant with a fasting glucose > 270 mg/dL, confirmed by repeat measure, and/or associated with symptoms of abdominal pain, nausea, vomiting or dehydration will trigger the recommendation to be

evaluated by the treating physician and the consideration of intensification of background glucose-lowering medication and/or initiation of new medication.

The above criteria are provided as a guideline. Investigators should always exercise his/her clinical judgement to protect participant's safety.

Medication changes and reasons for the changes will be documented on the eCRFs. Medications used to manage hyperglycemia are non-investigational and will not be provided by the sponsor.

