Proportion of treated patients with an HbA1c improvement of $\geq 0.5\%$ from baseline at 24 weeks (24 week score minus baseline score). Patients who fail to have HbA1c improvement of ≥ 0.5 points from baseline, for any reason, will be counted as not having achieved this endpoint.

Ninth Secondary Endpoint

The distribution of this endpoint is binary. Proportion of treated patients who achieve a HbA1c improvement of $\geq 0.5\%$ or more at 24 weeks from baseline and maintained at 48 weeks. Patients who fail to maintain HbA1c improvement $\geq 0.3\%$ at 48 weeks, for any reason, will be counted as not having achieved this endpoint. Patients who fail to achieve a HbA1c $\geq 0.5\%$ at 24 weeks will be excluded from the tabulation. The primary population for analysis of this endpoint will be the FAS population.

Proportion of treated patients with an HbA1c improvement $\geq 0.5\%$ from baseline at 24 weeks maintained at 48 weeks.

Tenth Secondary Endpoint: The distribution of this endpoint is continuous. The primary population for analysis of this endpoint will be the FAS population. Change in weight from baseline (post-baseline minus baseline) by visit. Weight change will be reported in both kilograms and %TBWL.

Eleventh Secondary Endpoint: Change in glucose-lowering medication usage.

Twelfth Secondary Endpoint: The distribution of this endpoint is continuous. The primary population for analysis of this endpoint will be the FAS population. Change in liver enzyme from baseline at 24 weeks (post-baseline minus baseline) for Alanine Aminotransferase (ALT).

Thirteenth Secondary Endpoint: The distribution of this endpoint is continuous. The primary population for analysis of this endpoint will be the FAS population. Change in liver enzyme from baseline at 24 weeks (post-baseline minus baseline) for Aspartate Aminotransferase (AST).

Fourteenth Secondary Endpoint: The distribution of this endpoint is continuous. The primary population for analysis of this endpoint will be the FAS population. Change from baseline in blood pressure by visit (systolic and diastolic run separately).

Fifteenth Secondary Endpoint: The distribution of this endpoint is continuous. The primary population for analysis of this endpoint will be the FAS population. Change in lipid profile from baseline by visit: total cholesterol

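### The NIS 'maintained at 48 weeks' HbA1c endpoint is scored without regard to glucose-lowering drugs added or increased after Week 24, when the protocol plans for them to be optimised

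*Protocol*

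**What the plan says.** **Medication rule.** Under Protocol 6.2.1, NIS background drugs return to their pre-procedure level and are "maintained stable until the Week 24 Visit has been completed". Changes needed for hypoglycaemia, hyperglycaemia or other safety reasons are allowed before then. After Week 24, "their glucose-lowering medications will be optimized as necessary to reach an HbA1c target of 7"%. Protocol 4.1 puts it a little differently: "glucose-lowering medications will be optimized to achieve individualized A1c goals, which for most individuals is a target of less than 7.0"%. SAP 5.1 carries a similar rule.

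**Endpoint.** Protocol 3 lists "Proportion of treated participants with an HbA1c improvement of 0.3% or more at 24 weeks from baseline and maintained at 48 weeks". The SAP's ninth secondary endpoint is the counterpart, an improvement "from baseline at 24 weeks maintained at 48 weeks". Its failure rule looks only at the Week 48 HbA1c. SAP 4.2.1 and SAP 9 use 0.3 and 0.5 in different places, which is a separate matter.

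**Analysis sets.** The mITT set (FAS in the SAP) has no medication condition. Per-Protocol requires participants to have "maintained stable glucose-lowering medications for 24 weeks post procedure". Completed Cases (SAP 6) adds only attendance at the Week 48 visit.

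**Medication data.** Change in use of glucose-lowering drugs is a separate secondary endpoint (Protocol 3; eleventh in the SAP), tabulated by visit in SAP Table 14.4.6. Protocol 6.2.3 adds: "Medication changes and reasons for the changes will be documented on the eCRFs".

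**The concern.** The endpoint asks whether a response seen at Week 24 is still there at Week 48. Between the two measurements the plan moves from stable drugs to drugs optimised as needed. Those most likely to be intensified are participants above target, who include responders whose HbA1c is rising again. A maintenance endpoint should pick out those participants, and the present scoring can count them as successes.

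The study has a single arm, so no control group passes through the same optimisation. The SAP's comparison sets contrast device generation, voltage and single versus double treatment, and the same medication rule applies to all of them. The Week 48 rate therefore describes the device together with optimised medication. The SAP allows its analyses to be used in regulatory submissions and manuscripts, where a maintained rate is likely to be read as durability of the device effect.

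**Working it through.** The plan gives no expected rate, power or assumed effect for this endpoint, so there is no planned figure to reproduce. Two checks apply.

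**1. Does reaching the drug target satisfy the endpoint?**

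Inputs: eligible baseline "HbA1C of 7.5-11.0% (58 - 97 mmol/mol), inclusive" (Protocol 5.1); target 7.0% (Protocol 6.2.1); thresholds 0.3 (Protocol 3) and 0.5 (SAP 9); mean baseline 8.6% in the first 27 treated participants (Appendix 4, section 1).

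Improvement at target = baseline − 7.0. Highest Week 48 HbA1c that still counts = baseline − threshold.

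| Baseline | Improvement at 7.0% | Highest value counted, 0.3 | Highest value counted, 0.5 |
|---|---|---|---|
| 7.5% | 0.5 | 7.2% | 7.0% |
| 8.6% | 1.6 | 8.3% | 8.1% |
| 11.0% | 4.0 | 10.7% | 10.5% |

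At every eligible baseline, a Week 24 responder brought to 7.0% meets both thresholds. Above the minimum baseline, values well short of target also count.

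**2. How far could the rate move?**

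Let p be the share of Week 24 responders who would hold their improvement on unchanged drugs, and q the share of the remainder kept above the threshold by optimisation. Then

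apparent maintained rate among responders = p + (1 − p) × q.

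Neither p nor q is in the documents; both are assumptions.

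- p = 0: the rate equals q, anywhere from 0% to 100%.
- p = 25%, q = 50%: 0.25 + 0.75 × 0.50 = 62.5%.
- p = 50%, q = 50%: 0.50 + 0.50 × 0.50 = 75%.
- p = 75%, q = 50%: 0.75 + 0.25 × 0.50 = 87.5%.

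For an illustrative 20 Week 24 responders with p = 50%, with exact 95% intervals:

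- q = 0: 10/20 = 50% (27% to 73%)
- q = 50%: 15/20 = 75% (51% to 91%)
- q = 100%: 20/20 = 100% (83% to 100%)

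These rates are among responders, which is the SAP's denominator. The protocol words the endpoint as a share of treated participants. On that denominator the rate cannot exceed the Week 24 response rate.

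**The case against.** Several points on the other side stand.

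- **Medication use is reported.** It has its own endpoint, a table by visit and a participant-level concomitant medication listing (SAP Listing 16.8.1). With the SAP's 20 patients, a reader could match drug changes to responder status by hand. What is missing is a pre-specified joint tabulation; the information itself is collected.
- **Week 24 already leads.** SAP 4.2.1 makes Week 24 the main time point for HbA1c, fasting glucose and HOMA-IR, which limits reliance on later values.
- **The endpoint is secondary and descriptive.** The primary endpoint is safety, Protocol 3 calls efficacy exploratory, and no text attributes the Week 48 rate to the device.

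A reader might also draw stronger conclusions that the documents do not support.

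- *Every NIS participant is titrated to 7%.* Protocol 6.2.1 says as necessary and Protocol 4.1 speaks of individualised goals.
- *The maintained rate will approach 100% whatever the device does.* That needs the SAP's responder-only denominator and near-universal success of optimisation. Protocol 1.1 says close to half of patients miss an HbA1c below 7%, and this cohort is already uncontrolled on one to four drugs. Missing 7.0% does not settle the matter, though, since the table above shows that much less can be enough to count.
- *Week 24 is unconfounded.* Drug changes for safety are permitted earlier (Protocol 6.2.1, 6.2.3), mITT/FAS keeps those participants, everyone receives lifestyle counselling, and there is no control arm.
- *Scoring any intensified participant as a failure isolates durability.* From 8.6%, a fall of 1.6 points is needed to reach 7.0%. The two hydrothermal ablation studies described in Protocol 1.2 report mean falls of 1.2 and 0.9 points at about six months, which from 8.6% would leave 7.4% and 7.7%. Participants who hold such a response remain above 7.0% and may be intensified under the plan, so this version is biased downward.

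**Conclusion.** The point holds for the NIS cohort and for the part of the endpoint that runs from Week 24 to Week 48, together with the Week 36 and 48 changes. As planned, these results cannot separate persistence of the device effect from the effect of optimised drugs, and no analysis set or planned tabulation does so. That conclusion rests on the medication rule, the scoring rule and the eligibility floor of 7.5%, all of which are in the documents.

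The direction is clear for one kind of participant: a responder who loses the effect and is brought to 7.0% by drugs is counted as maintained. The amount is unknown, because p and q are assumptions. The primary safety endpoint is not affected. The insulin cohort has its own endpoint and its own medication rules in Appendix 4 and is outside this point. The SAP names a REGENT-1-US study (Doc. No. 346), but the point stands on the protocol alone.

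**What to change.** Change the analysis and labelling only; clinical management stays as it is.

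1. Keep the all-comers maintained rate, label it as device plus optimised medication, and state its denominator.
2. Cross-tabulate Week 48 maintenance by medication status versus baseline: reduced, unchanged, new or increased. Fix before database lock how a participant with both a reduction and an increase is classified.
3. Show the Week 36 and Week 48 HbA1c changes by the same three categories. These are descriptive: status is decided after treatment and partly by HbA1c, so differences between categories are not treatment effects.
4. Report maintenance without any new or increased glucose-lowering drug as a supplementary conservative figure. Say beside it that it is biased downward, because participants who hold their response but remain above target may also be intensified.
5. Describe Week 24 as the last time point before planned optimisation, not as unconfounded.

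The data are already collected: diabetes medication review is scheduled at every follow-up visit to Week 48 (Protocol Appendix 2) and changes go on the eCRF. The cost is a few extra tables, a less favourable supplementary figure and small cells. The SAP's device groups are 3, 7 and 10 patients, so the split is best shown for all patients combined.
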